7.3 Criteria for removal from treatment

- 7.3.1 If a carious lesion is arrested or remineralizes in any treatment group, this is considered a stable lesion. The patient will continue on with that treatment modality (ie. reapplication at 3 months, 6 months, and 12 months) until the tooth exfoliates or other comprehensive dental treatment is required. That lesion will continue to be monitored for any change in progress.
- 7.3.2 Treatment will be discontinued if a patient experiences any persistent eye, skin, oral mucosa, respiratory, and gastrointestinal irritation that are considered Grade 2 and above adverse events.
- 7.3.3 Treatment will be discontinued if a patient experiences any allergic reactions or sensitivities to SDF.
- 7.3.4 Patients will discontinue treatment if or when a carious lesion progresses to ICCMS category 4 or beyond. The patient will be notified and scheduled for routine operative dental procedures (ie. restorations) to treat the carious lesion.
- 7.3.5 Treatment will be discontinued if patient becomes intolerant to SDF or their behavior does not allow for safe and proper application of protocol.
- 7.3.6 A patient may always be removed from treatment whenever he/she wishes.

9.0 CLINICAL EVALUATIONS AND STUDY CALENDAR

Dental Prophy (cleaning)		Х		Х
SDF application (with or without use		X ¹	X ¹	X ¹
of Super Floss)				
Fluoride varnish application*		Х	X	Х
Parameter				
Comprehensive Medical and Dental	Х			
History				
Updated Medical and Dental History			Х	Х
Oral Examination	Х		Х	Х
Dental Radiographs	Х			Х
Assessment and Treatment Planning	Х			Х
Informed Consent/Assent				
Dental Prophy (cleaning)	Х			Х
SDF application (with or without use		1	X^1	X ¹
of Super Floss)				
Fluoride varnish application*	Х		Х	Х

1 SDF application with or without the use of Super Floss is determined by which treatment group the patient is in.

* All treatment groups will get fluoride varnish application.

10.0 CRITERIA FOR EVALUATION AND ENDPOINT DEFINITIONS

The primary outcome is arrest of interproximal caries on a primary molar, as measured by lack of change in ICCMS classification indicating caries progression on radiographic examination, (higher score indicates progression). The outcome will be evaluated at three time points: baseline, 6 months and 12 months. As the treatments cannot be made to appear similar to one another, neither the treating dentist or the patient/parent(s) will be blinded to treatment status. However, evaluation of the outcome will made by comparing time lapse (ie. comparing intial xrays vs. at 6 months vs. at 1 year) bitewing radiographs and visualizing if the carious lesion has remineralized, arrested, or progressed

11.0 SPECIAL INSTRUCTIONS:

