- 3.3 Follow-Up: Recall examinations and treatment reapplication will be done at 3 months, 6 months, and 12 months after the initial visit in accordance with current American Academy of Pediatric Dentistry (AAPD) guidelines for high caries risks patients⁵. Bitewing radiographs will be taken at 6 months and 12 months. This is in accordance with the "Prescribing Dental Radiographs..." guidelines as approved by the AAPD²⁰, which state that bitewing radiographs in high risk children with dental caries are recommended every 6-12 months.
- 3.4 Providers: Residents and Attendings at the Ostrow School of Dentistry at USC, Pediatric Residency Program. All residents and attendings participating in this study will be trained and standardized on how to identify lesions of interest on radiographs, obtain consent, and apply the medications.
- 3.5 Tracking of study participants: We will count the number of participants who:
 - 1. Those who are asked to participate
 - 2. Those who consent
 - 3. Those who drop out before randomization/after randomization
 - 4. Those who withdraw by their own choice for various reasons
 - 5. Those who are lost to follow up

Note: We will only collect and store clinical data for those participants who continue throughout the duration of the project. If a participant decides to drop out of the study at any time, then we will no longer collect data from the medical record during their ongoing clinical care. We will also discard any previous data we have collected on the participants that drop out.

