the relationship between these two variables using generalized estimating equations, specifying a Poisson (or negative binomial, if overdispersed) family and a log link. We will also specify an exchangeable correlation matrix and a robust standard error.

Since the study is randomized, we do not anticipate needing to adjust for any confounders. However, should we find any differences in demographic or clinical variables at baseline, we will investigate them as potential confounders, which will be defined as those variables which alter the odds ratio by >15% when included in the model.

For those with missing data on outcomes or other covariates to be included in the model, we will consider multiple imputation methods if the amount of missing data is <10%. To assess the impact of missing data, we will compare those with missing data to those not missing data with respect to demographic and clinical variables to assess comparability. Should imputation be utilized, a sensitivity analysis will be conducted excluding those for whom data was imputed to assess the impact of imputation.

Model fit will be evaluated by inspection of residuals and influential points. As we are conducting an interim analysis, we will use a two-sided Bonferroni-corrected p-value of a=.025 for statistical significance. Finally, to assess the degree to which the two raters agree with respect to classifying the outcome of the x-rays, we will calculate and report Kappa. All statistical analyses will be done using Stata 15.0 (College Station, TX).

Power Analysis

We calculated power using a cluster-randomized design. We were unable to locate any previous studies examining the impact of these three treatments (or any two) using the same classification system as our outcome. However, we were able to obtain an estimate of 0.0 to 0.25 for the interclass correlation coefficient (ICC) (Honkala et al., 2011). Assuming the mean ICC, and assuming a clinically significant mean difference of 0.2, a standard deviation of 0.2, a covariance of cluster sizes of 0.65, two caries on average per child, and a two-sided adjusted Type I error rate of 0.025 to account for the three time points at which the data will be analyzed, we will have 80% power with 11-12 participants per group, for a total of 33-36 participants (66-72 caries). Since we anticipate significant loss-to-follow-up over the course

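### The plan does not mask the two radiograph raters to arm or separate them from the treating providers, although the trial is open label and the primary outcome is a visual judgement

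*Combined protocol and SAP*

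**What the plan says.** Section 10.0 states that "neither the treating dentist or the patient/parent(s) will be blinded to treatment status", because the treatments cannot be made to look alike. The next sentence opens with *However* and says that "evaluation of the outcome will made by comparing time lapse" bitewings from baseline, 6 months and 1 year, and by "visualizing if the carious lesion has remineralized, arrested, or progressed".

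Section 13.0 makes the change in ICCMS category from baseline to 12 months the primary outcome, with an interim analysis at 6 months. It hypothesises that the SDF with Super Floss group will do best, followed by SDF without it. It plans a Kappa statistic "to assess the degree to which the two raters agree with respect to classifying the outcome of the x-rays".

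Section 3.4 says that participating residents and attendings will be "trained and standardized on how to identify lesions of interest on radiographs", as well as in obtaining consent and applying the study agents. It does not name them as the outcome raters.

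No section says who the two raters are, whether they treat study children, whether they are masked to arm, whether films are de-identified, or how disagreements are settled.

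**The concern.** The outcome is a call on whether a radiolucency has moved by a category, and the plan names the arm expected to win. If a reader knows the arm, expectation can tilt borderline calls toward it. That tilt enters the estimated difference directly. The exchangeable correlation and robust standard error in 13.0 deal with clustering and do not correct a shifted mean. Kappa measures agreement, so two readers who lean the same way can agree well.

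The placement of the *However* sentence matters. A statement that the readers are masked would belong there, and a team could take the time-lapse comparison as serving that purpose. It does not. The follow-up films must also be read for care, since sections 5.3.2 and 7.3.4 act on lesions that pass Category 3. Nothing in the plan separates that chairside reading from the outcome reading.

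**Working it through.** **Inputs, all from the Power Analysis in 13.0:** mean difference 0.2; SD 0.2; ICC 0.0 to 0.25, mean 0.125; cluster-size variation 0.65 (the plan calls it a covariance; read here as a coefficient of variation, CV); m = 2 lesions per child; two-sided alpha 0.025 (critical value 2.2414); power 80% (0.8416).

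**Step 1. Reproduce the plan's sample size.**
- Lesions per arm without clustering: 2 × [0.2 × (2.2414 + 0.8416) / 0.2]² = 19.01.
- Design effect: 1 + [(CV² + 1) × m − 1] × ICC = 1 + [(0.4225 + 1) × 2 − 1] × 0.125 = 1.2306.
- Children per group: 19.01 × 1.2306 / 2 = 11.70, so 12. Without the CV term the figure is 10.69, so 11.
- Power is 77.3% at 11 and 81.1% at 12 per group. The stated 11-12 per group reproduces, so the same inputs can be used below.

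**Step 2. Effect of a reading shift when the treatments do not differ.** Let b be the between-arm shift in mean ICCMS change caused by reading alone. The documents give no value for b, so it is an assumption. A shift of 0.10 corresponds to a one-category misreading of 10% of lesions in one arm only.
- SE = 0.2 × √[2 × 1.2306 / (2k)] for k children per group. At k = 12, SE = 0.0640.
- False-positive rate = P(|Z + b/SE| > 2.2414).
- Example, k = 12 and b = 0.10: b/SE = 1.561 and 2.2414 − 1.561 = 0.680, giving 24.8%.

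| Shift b (categories) | k = 10.4 | k = 12 | k = 20 |
|---|---|---|---|
| 0 | 2.5% | 2.5% | 2.5% |
| 0.02 | 3.1% | 3.2% | 3.7% |
| 0.05 | 6.6% | 7.3% | 10.9% |
| 0.10 | 21.6% | 24.8% | 41.1% |

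Here k = 20 is the 60 recruits divided by three, and k = 10.4 is what remains of them after 48% loss (60 × 0.52 / 3). The inflation grows with k, because more children shrink the SE and leave b unchanged.

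**Step 3. Sensitivity to the planned SD.** Step 2 relies on the SD of 0.2. If the outcome is instead analysed as arrest yes/no, the variance is larger. Assume 50% to 70% arrest in one arm and add b to the other. The effective number of lesions per arm is 24 / 1.2306 = 19.5, and SE = √{[p(1 − p) + (p + b)(1 − p − b)] / 19.5}. At 12 per group:
- b = 0.05 gives 3.2% to 3.4%.
- b = 0.10 gives 5.6% to 6.6%.

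At 20 per group the corresponding figures are 3.7% to 4.0% and 7.8% to 9.7%. The direction is the same, but the size is much smaller than on the plan's own SD.

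**The case against.** The strongest reply is that the documents do not say the raters are unmasked. Section 10.0 lists only the treating dentist and the family as unblinded, and *However* may be meant to introduce the radiographic reading as the protected part. That stands: this is a procedure left unstated, not an unmasked reading chosen by design.

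A reader might also infer from 3.4 that the treating residents and attendings are the raters. The text does not support that. Training to identify lesions fits screening and delivery equally well, and 13.0 does not identify the raters. The plan permits treaters to rate; it does not specify it.

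A reader might further infer that knowing the film order creates a difference between arms. If the reader does not know the arm, order should affect all arms alike, so knowledge of arm is what matters. Nor can the order of the 6- and 12-month films be concealed at the interim reading, because the 12-month films do not yet exist.

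Finally, any figure for the bias rests on assumption. Section 13.0 reports that no ICCMS progression or remineralization rates were found. A one-step change in 30% to 50% of lesions would have an SD of √[p(1 − p)], or 0.46 to 0.50, against the planned 0.2, so the steepest figures above may overstate the effect. This limits the magnitude but does not supply the missing safeguard.

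**Conclusion.** The point holds as a gap in the plan. The trial is open label with a favoured arm and a visually judged primary outcome, and no section masks the two raters or separates them from treatment. Scoring with knowledge of arm would comply with the text, and neither Kappa nor the cluster adjustment would detect or remove the result.

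The size of any bias is unknown. For an assumed shift of 0.05 to 0.10 category, the false-positive rate at 12 per group would be about 7% to 25% instead of 2.5% with the plan's SD of 0.2, and about 3% to 7% on an arrest yes/no scale with 50% to 70% arrest. These figures rest on a normal approximation, an ICC of 0.125, and a shift in one arm only. They show why a target of 0.2 category leaves little room for reading error and are not an estimate for this trial. The documents do not support saying that the readers are unmasked, that treaters are the raters, or that film order alone would produce a difference.

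**What to change.** In 10.0, replace the *However* sentence with a statement that:
- the two planned raters, identified by role, score the bitewings independently from coded image files with child identity and arm removed;
- where feasible, a rater does not score a child he or she treated;
- the primary and interim analyses use these masked scores, which are kept separate from the chairside clinical reading;
- any film not originally scored masked is re-read under the same conditions.

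A line on how disagreements between raters are settled would complete the text. Concealing film order is optional and cannot apply to the 6-month interim reading.

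The cost is a protocol edit, coding of image files and some re-reading. Two raters are already planned, so masking itself needs no extra reader. The words *where feasible* matter if raters also treat, because a strict bar could leave some children without two eligible raters for Kappa. Sample size, treatment and visits do not change. If the raters are already masked and independent, one sentence saying so settles the point.

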11.1 Not applicable

12.0 DATA COLLECTION AND MONITORING

As the study is small and preliminary in nature, there are is no formal monitoring committee. However, the statistician will monitor the progress of the study to assess accrual rate and data quality throughout the progress of the study. Once collected, the data will be cleaned, beginning with range checks, evaluation of outliers, crosstabs between variables of interest and visual examinations.

13.0 STATISTICAL CONSIDERATIONS

- 13.1 The proposed pilot Phase III randomized controlled clinical trial aims to determine which of the following treatments is superior in arresting dental caries among patients presenting with interproximal caries scoring RA1 RA3 on the International Caries Classification and Management System (ICCMS): (1) Fluoride varnish (FV, current standard of care, control), (2) Super floss + SDF + FV, (3) SDF + FV. We hypothesize that group 2 will have the best outcomes, as measured by no change or reversal in ICCMS classification indicating no caries progression or remineralization on radiographic examination, (higher score indicates progression) followed by group 3. As we could find no data on ICCMS-defined progression or remineralization rates for either Super Floss or fluoride, we were unable to calculate power. Instead, we provide estimates of recruitment based on feasibility. We expect to accrue approximately 20 participants, with 2 qualifying teeth per participant, in each group.
- 10% loss to follow up has increased dramatically to ~48%. Given this unexpected setback, we now need to continue recruiting participants to reach sufficient power. We originally planned to enroll 39 subjects in the study, but would now like to add 21 new participants for a total of 60 participants.

Descriptive statistics will be calculated for all demographic and clinical characteristics to assess the degree to which randomization was successful using means and standard deviations or medians and interquartile ranges for continuous variables and counts and percentages for categorical variables.

The primary analysis will be by intent-to-treat. The primary outcome is the change in ICCMS category, as assessed by radiographic evidence, from baseline to 12 months, with a planned interim analysis to evaluate the endpoint at 6 months for early indications of efficacy. We will calculate the median difference at each time point and use an individual-level model with an adjustment to the standard error to account for the clustering. First we will evaluate the association between treatment groups and the change in ICCMS score from baseline at 6 and 12 months using a cluster-adjusted chi-squared test. We will further assess

14

the relationship between these two variables using generalized estimating equations, specifying a Poisson (or negative binomial, if overdispersed) family and a log link. We will also specify an exchangeable correlation matrix and a robust standard error.

Since the study is randomized, we do not anticipate needing to adjust for any confounders. However, should we find any differences in demographic or clinical variables at baseline, we will investigate them as potential confounders, which will be defined as those variables which alter the odds ratio by >15% when included in the model.

For those with missing data on outcomes or other covariates to be included in the model, we will consider multiple imputation methods if the amount of missing data is <10%. To assess the impact of missing data, we will compare those with missing data to those not missing data with respect to demographic and clinical variables to assess comparability. Should imputation be utilized, a sensitivity analysis will be conducted excluding those for whom data was imputed to assess the impact of imputation.

Model fit will be evaluated by inspection of residuals and influential points. As we are conducting an interim analysis, we will use a two-sided Bonferroni-corrected p-value of a=.025 for statistical significance. Finally, to assess the degree to which the two raters agree with respect to classifying the outcome of the x-rays, we will calculate and report Kappa. All statistical analyses will be done using Stata 15.0 (College Station, TX).

Power Analysis

We calculated power using a cluster-randomized design. We were unable to locate any previous studies examining the impact of these three treatments (or any two) using the same classification system as our outcome. However, we were able to obtain an estimate of 0.0 to 0.25 for the interclass correlation coefficient (ICC) (Honkala et al., 2011). Assuming the mean ICC, and assuming a clinically significant mean difference of 0.2, a standard deviation of 0.2, a covariance of cluster sizes of 0.65, two caries on average per child, and a two-sided adjusted Type I error rate of 0.025 to account for the three time points at which the data will be analyzed, we will have 80% power with 11-12 participants per group, for a total of 33-36 participants (66-72 caries). Since we anticipate significant loss-to-follow-up over the course

of the study, we will inflate the sample size by ~48% and recruit a total of 54-60 participants (108-120 caries). Sample size was calculated using PASS Software v.14.0 (Kayesville, UT).

This study is powered to detect an effect in a population of children who are predominantly non-white. Therefore, the sample size as calculated is likely to result in a sample size with reasonable power to detect an effect near the size outlined above, if perhaps slightly larger.

14.0 REGISTRATION GUIDELINE

- 14.1 Participants will be randomized as described in Section 6.3. Randomization envelopes will be available to the investigators, who need only select the next one in the series to accomplish randomization. No stratification parameters have been specified.
- 14.2 The forms and records needed for registration: Informed Consent; Assentfor Younger Subjects ; and Tracking Form.

Note: At the time of registration, two copies of a signed and dated patient Informed Consent form with Bill of Rights must be available (a copy for patient's dental chart; a copy for the subject/parent; and the original for the PI's file).

15.0 BIOHAZARD CONTAINMENT

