5.0 SELECTION AND WITHDRAWAL OF SUBJECTS

- 5.1 Inclusion Criteria:
 - 5.1.1 ASA I and ASA II children, aged 3-12, with interproximal decay on deciduous molars identified by radiographs. These teeth will not have previous restorations.
 - 5.1.2 Radiographic decay within enamel or extending to the dentin-enamel junction based on International Caries Classification and Management System (ICCMS)¹⁸ Categories 1 through 3 see above. Categories 1, 2 and 3 signify the extent of the "Initial Stages" of an interproximal carious lesion with radiolucency in the outer 1/2 of enamel, inner 1/2 of enamel, and outer 1/3 of dentin respectively.
 - 5.1.3 Interproximal lesions present without existing restorations, recurrent decay, or adjacent teeth with existing restorations.
 - 5.1.4 Behavior of the children should be within a Frankl 3 or 4 category²¹, indicating a "Positive" and "Definitely Positive" behavior rating, which would allow for safe and controlled execution of the proposed protocol.
- 5.2 Exclusion Criteria:
 - 5.2.1 Children who are not ASA I or ASA II.

- 5.2.2 Children who are allergic to or intolerant of SDF
- 5.2.3 Children who have known sensitivity to silver or heavy metal-ions, or have abnormal skin sensitization.
- 5.2.4 Children who have ulcerative gingivitis or stomatitis.
- 5.2.5 Carious interproximal lesions on primary molars in ICCMS Category 4, 5, or 6¹⁸, which signify the extent of the carious lesion radiographically reaching the middle 1/3 of dentin, inner 1/3 of dentin, and into the pulp respectively.
- 5.2.6 Behavior of a child within the Frankl 1 or 2 category²¹, indicating a "Definitely Negative" and "Negative" behavior, which may compromise safe application of SDF.
- 5.3 Withdrawal Criteria
 - 5.3.1 Patients can withdrawal voluntarily at any time.
 - 5.3.2 Any tooth which has progression of caries beyond ICCMS Category 3 will be withdrawn from the study. These teeth will be treated with appropriate restorative dental treatment according to the standard of care.
 - 5.3.3 Any qualifying tooth that subsequently requires a restoration or extraction due to trauma or exfoliates prematurely will be withdrawn from the study.
 - 5.3.4 Any study tooth whose adjacent tooth exfoliates before the end of this study and exposes the interproximal contact will be withdrawn from the study.

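### No joint model of the 6- and 12-month scores is specified, so a tooth without a 12-month film adds nothing to the primary 12-month test, even when it is a known failure at 6 months

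*Combined protocol and SAP*

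**What the plan says.** - **Endpoint and films.** Section 13.1: "The primary outcome is the change in ICCMS category, as assessed by radiographic evidence, from baseline to 12 months", with an interim look at 6 months. Section 3.3: "Bitewing radiographs will be taken at 6 months and 12 months".
- **Summary and first test.** Section 13.1 says "We will calculate the median difference at each time point". It then tests the association of treatment group with "the change in ICCMS score from baseline at 6 and 12 months using a cluster-adjusted chi-squared test".
- **Model.** The plan next assesses "the relationship between these two variables using generalized estimating equations", with a Poisson or negative binomial family and a log link. It adds: "We will also specify an exchangeable correlation matrix and a robust standard error". It states no visit term, no arm-by-visit term and no cluster unit, and does not say which visits enter the model.
- **Analysis set and missing data.** "The primary analysis will be by intent-to-treat". Multiple imputation is only to be considered, and only if less than 10% of data are missing. The same section puts loss to follow-up at about 48%.
- **Tooth-level withdrawal.** Section 5.3.2 withdraws a tooth that progresses beyond category 3. Section 5.3.3: "Any qualifying tooth that subsequently requires a restoration or extraction due to trauma or exfoliates prematurely will be withdrawn from the study". Section 5.3.4 withdraws a tooth whose contact is exposed when its neighbour exfoliates. None of these says what becomes of the tooth's 6-month score.
- **Child-level drop-out.** The note under section 3.5 says data already collected on participants who drop out will be discarded.

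**The concern.** The trial enrols deciduous molars in children aged 3 to 12, so some exfoliation within a year is foreseeable, and section 5.3 takes out single teeth without saying that the child leaves. Such a tooth can have a valid 6-month score and no 12-month score. The 12-month chi-squared test cannot use it, and no model that could use it is clearly specified.

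Two things are at stake. The smaller is precision: a 6-month change carries information about the 12-month change, and the trial is small. The larger is selection. A tooth withdrawn under 5.3.2 at 6 months is missing at 12 months because of its outcome. If one arm has more early progression, that arm loses more of its failures before the primary comparison, which pulls the arm difference towards zero.

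**Working it through.** **1. The plan's own figure.** Inputs from the Power Analysis in section 13: difference 0.2, SD 0.2, two-sided alpha 0.025, power 80%, ICC 0.125 (mean of 0.0 and 0.25), two lesions per child, and 0.65 read as the coefficient of variation of cluster size.
- Lesions per arm: 2 × ((2.241 + 0.842) × 0.2/0.2)² = 19.01.
- Design effect: 1 + ((0.65² + 1) × 2 − 1) × 0.125 = 1.231.
- Children per arm: 19.01 × 1.231 / 2 = 11.7, which agrees with the stated 11-12.
- With 60 recruited and 48% lost, 60 × 0.52 / 3 = 10.4 children per arm remain, with 74.7% power on the same formula. That is loss of children; it sets the scale but is not the loss examined here.

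**2. Gain from a joint model.** Let f be the share of lesions scored at 6 months that lack a 12-month film, and r the correlation between the 6- and 12-month changes. Treating lesions as independent and r as known,

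Var(joint) / Var(12-month only) = 1 − r² × f.

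**3. Inputs not in the documents.** Neither f nor r is given. If the 12-month change is the sum of two independent half-year changes of equal variance v, then r = v / √(v × 2v) = 0.71 and r² = 0.5. For f, 10%, 20% and 30% are assumed.

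| f | r | variance ratio | fall |
|---|---|---|---|
| 0.10 | 0.71 | 1 − 0.5 × 0.10 = 0.95 | 5% |
| 0.20 | 0.71 | 1 − 0.5 × 0.20 = 0.90 | 10% |
| 0.30 | 0.71 | 1 − 0.5 × 0.30 = 0.85 | 15% |
| 0.20 | 0.5 | 1 − 0.25 × 0.20 = 0.95 | 5% |
| 0.20 | 0.8 | 1 − 0.64 × 0.20 = 0.87 | 13% |

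At r = 0.71 this is worth 1/0.95 = 1.05 to 1/0.85 = 1.18 times as many lesions.

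**4. Allowing for clustering.** Take two lesions per child, ICC 0.125, films missing independently by lesion, and a correlation of 0.125 × r between one lesion's 6-month change and the other's 12-month change. The ratio becomes 1 − r² × f × (1 − 0.125 × (1 − f)). With r² = 0.5:
- f = 0.10: 1 − 0.05 × 0.8875 = 0.956
- f = 0.20: 1 − 0.10 × 0.90 = 0.910
- f = 0.30: 1 − 0.15 × 0.9125 = 0.863

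The falls are 4%, 9% and 14%, so the simple formula is only slightly generous.

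**5. Model class.** An illustrative simulation with 10 children per arm and assumed rates gave a fall of about 3-13% for a likelihood-type joint estimate under random tooth loss. An exchangeable GEE with a visit term gained only 0-6%, because one common correlation does not separate visits within a lesion from lesions within a child. When teeth that had progressed at 6 months were withdrawn, the 12-month effect was attenuated by roughly 12-15%. The likelihood-type estimate removed most of that; the exchangeable GEE left most of it.

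**6. Children who drop out.** Under the note in section 3.5 their 6-month scores no longer exist for any model, so the gain from them is zero.

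**The case against.** **The GEE may already be joint.** A reader might infer that every analysis is done visit by visit. The text does not settle that. The two variables in the GEE could be treatment and change at one visit or at both, and the plan writes out no model terms at all, so a missing visit term proves little. The sentence on medians concerns only a descriptive summary. This stands: the supportable criticism is that the chi-squared test reads as one test per visit and the GEE is unspecified. The remedy helps either way, since a pooled GEE without a visit term would not isolate the 12-month contrast.

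**Imputation could use the 6-month scores.** If drop-outs are discarded, what remains missing is mainly tooth-level and might fall below 10%. This stands in part, but imputation is only to be considered, and the chi-squared test as described does not use it.

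**The 6-month score may not be kept.** Correct. Section 5.3 is silent, so the plan has to say so.

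**A joint model might seem to rebuild the 10.4 children per arm.** A reader might infer this from the 48% loss. The documents do not support it: the section 3.5 note removes the films that would be needed.

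**Some 12-month values would be hypothetical.** After exfoliation or exposure of the contact there is no interproximal contact lesion left to score, so a joint model estimates what would have been seen had the tooth and contact remained. This stands as a limitation to be stated.

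**A 12-month-only comparison is a legitimate choice in a small preliminary trial.** True, but it then needs a rule for teeth withdrawn under 5.3.2. The intent-to-treat statement gives them no 12-month value.

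**Conclusion.** The point holds as one of under-specification with a modest cost. As described, the primary 12-month test takes nothing from a tooth scored only at 6 months, and it leaves out teeth already known to have failed. On precision, the gain from a joint model is about 5-15% lower variance (4-14% with the plan's mean ICC), assuming 10-30% tooth-level loss after the 6-month film and r of about 0.7. At 20% loss it is 5-13% for r from 0.5 to 0.8. These inputs are assumptions, and if tooth-level loss is small the gain is small.

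The selection under 5.3.2 matters more than the precision. Its size cannot be derived from the documents, because they give no progression rates; the 12-15% attenuation is illustrative only. No gain can be claimed for children who drop out unless the section 3.5 discard rule is reconciled with intent-to-treat. This is a worthwhile improvement rather than a flaw that invalidates the plan.

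**What to change.** In section 13.1, for the final analysis:
- Fit one likelihood-based longitudinal model (such as a mixed model), or a suitably weighted one, to the 6- and 12-month scores together. Include arm, visit and arm × visit, with correlation for lesions within child and for visits within lesion. Take the 12-month arm contrast as primary. Simply extending the unweighted exchangeable GEE is not enough, since it generally needs data missing completely at random.
- State that 6-month scores of teeth withdrawn under section 5.3 are kept.
- Report two sensitivity analyses: the 12-month-only comparison, and one that counts teeth withdrawn under 5.3.2 as progressed.
- Leave the 6-month interim look as planned.
- Reconcile the discard note under section 3.5 with the intent-to-treat statement.

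Cost: SAP wording and a little more modelling on films already planned. Downsides: a few more parameters in a small sample, a missing-at-random assumption for lesions without a 12-month film, and a hypothetical 12-month value for exfoliated teeth and exposed contacts.
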